Appendix B: Interim Analysis Plan

This section describes definitions of analysis sets, key efficacy endpoints and statistical methods for the interim analyses (IAs). Further details of the interim analysis are included in the URC charter.

The first interim analysis may occur after 50% of participants have completed at least 6 weeks of treatment or at a time selected by the sponsor, and a second interim analysis may be performed after 100% of participants have completed at least 6 weeks of treatment or at a time selected by sponsor / percentage of participants with a planned week 6 visit before data cut selected by sponsor. The objective of the administrative interim analyses will be to decide if an CCI zibotentan/dapagliflozin project activities CCI on the interim data.

The decision-making framework of the interim analyses is based on CCI

B.1. Analysis Sets

The analysis sets are defined as follows.

Analysis Set	Data selection as indicated in Table 4	Description	Data Period
First Administrative Interim FAS	M	All participants who were randomised at least 44 days ago i.e. reached study day 45, and who have received any study treatment at the time of the first interim analysis data cut-off. Participants are evaluated according to the treatment assigned at randomisation.	Baseline to Week 6 data
First Administrative Interim Safety Analysis Set	M	All participants who have received any study treatment at the time of the first interim analysis data cut-off. Participants are evaluated according to the actual treatment they received.	All data
First Administrative Interim All Randomised Set	M	All participants who are randomised at least 44 days ago i.e. reached study day 45 at the time of the first interim analysis data cut-off. Participants are evaluated according to the treatment assigned at randomisation.	Baseline to Week 6 data
Second Administrative Interim FAS	M	All participants who were randomised at least 44 days ago i.e. reached study day 45, and who have received any study treatment at the time of the second interim analysis data cut-off. Participants are evaluated	Baseline to Week 6 data*

		according to the treatment assigned at randomisation.	
Second Administrative Interim Safety Analysis Set	M	All participants who have received any study treatment at the time of the second interim analysis data cut-off. Participants are evaluated according to the actual treatment they received.	All data
Second Administrative Interim All Randomised Set	M	All participants who are randomised at least 44 days ago i.e. reached study day 45 at the time of the second interim analysis data cut-off. Participants are evaluated according to the treatment assigned at randomisation.	Baseline to Week 6 data*

*Some outputs will be based on longer data periods (not just baseline to Week 6)

B.2. Fluid-related Analysis

Changes in fluid-related measures (weight gain or BNP) meet the defined threshold to be reported as an event of special interest if they meet the criteria defined in Section 3.2.2.7.

In the examination of the fluid-related safety CCI [REDACTED]
[REDACTED] The examination depends on the actual number of participants with a fluid-related event of special interest and the total number of participants in the zibotentan/dapagliflozin arm and in the dapagliflozin 10 mg monotherapy arm.

Assuming CCI participants in each arm for the first interim analysis, the scenario analysis is illustrated below where the CCI is used to estimate CCI [REDACTED]

CCI [REDACTED]

This will be performed for zibotentan/dapagliflozin 1.5/10 mg vs dapagliflozin 10 mg as well as for zibotentan/dapagliflozin 0.25/10 mg vs dapagliflozin 10 mg.

B.3. Efficacy Analysis

In the administrative interim analyses, the primary efficacy endpoint is the UACR reduction difference from baseline to Week 6, where the comparison will be made for each active zibotentan

arm (1.5 mg and 0.25 mg) vs the dapagliflozin 10 mg monotherapy arm. The UACR reduction will be analysed by means of the MMRM approach as described in Section 4.10.2.2 using the Administrative Interim FAS. The least square estimate of the dapagliflozin-adjusted UACR reduction and its SE will be used CCI

[REDACTED] UACR reduction difference.

The CCI [REDACTED] in terms of the UACR reduction difference are calculated as CCI [REDACTED]

CCI [REDACTED]

In total, 2 CCI [REDACTED] will be created:

- UACR reduction difference at Week 6 for zibotentan/dapagliflozin 1.5/10 mg vs dapagliflozin 10 mg
- UACR reduction difference at Week 6 for zibotentan/dapagliflozin 0.25/10 mg vs dapagliflozin 10 mg

CCI [REDACTED]

CCI [REDACTED]

With reference to the CCI, the URC will evaluate CCI

CCI

Note that the above will be done for each active treatment arm in the main analyses, zibotentan/dapagliflozin 1.5/10 mg and zibotentan/dapagliflozin 0.25/10 mg, CCI

B.4. General Safety Analysis

General safety analysis will be based on the Administrative Interim Safety Analysis Set. Selected safety outputs will be presented by treatment arm and overall.

A summary of AEs in any category will be presented by treatment. The number and percentage of participants reporting AEs, SAEs and AEs leading to discontinuation of study treatment in each treatment arm will be tabulated by SOC and PT, sorted in decreasing overall (across treatments) frequency.

Listings may be presented of participants with SAEs, AEs leading to discontinuation of study treatment, and participants who died. A listing may be presented of participants with AEs, detailing whether these are SAEs, AEs leading to discontinuation of study treatment, or result in death.

Summary statistics of laboratory data (as described in Section 4.11.4) will be presented. Participants with laboratory values which are highlighted as abnormal will be listed. Summary statistics of vital signs and ECG data will be summarised (as described in Section 4.11.5).

Reference:

CCI

Appendix C: Treatment-Emergent Changes in Relevant Laboratory Parameters

The treatment-emergent changes in relevant laboratory parameters for this study are as follows:

Laboratory Parameter	Range	Limits
Creatinine		≥1.5xBaseline Serum Creatinine ≥2xBaseline Serum Creatinine
Sodium		<120 mmol/L <130 mmol/L >150 mmol/L
Potassium		≤2.5 mmol/L ≥6.0 mmol/L
Creatine Kinase		>5xULN >10xULN
Haemoglobin		<9 g/dL

SIGNATURE PAGE

This is a representation of an electronic record that was signed electronically and this page is the manifestation of the electronic signature

Document Name: d4325c00001-sap-ed-3		
Document Title:	Statistical Analysis Plan Edition 3	
Document ID:	Doc ID-004471786	
Version Label:	3.0 CURRENT LATEST APPROVED	
Server Date (dd-MMM-yyyy HH:mm 'UTC'Z)	Signed by	Meaning of Signature
08-May-2023 08:50 UTC	PPD [REDACTED]	Content Approval
05-May-2023 18:27 UTC	PPD [REDACTED]	Author Approval

Notes: (1) Document details as stored in ANGEL, an AstraZeneca document management system.

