5.1 Inclusion Criteria

Participants are eligible to be included in the study only if all of the following criteria apply:

Age

- 1 Participant must be 18 years of age or older at the time of signing the informed consent.

Type of Participant and Disease Characteristics / Laboratory Parameters

- 2 Diagnosis of CKD, defined as:
 - (a) eGFR (CKD-EPI) ≥ 20 mL/min/1.73 m² (by CKD-EPI formula, see Section 8.1.2.2)
AND
 - (b) Urine albumin to creatinine ratio (UACR) ≥ 150 and ≤ 5000 mg albumin/g creatinine, based on a single first morning void spot urine sample at screening.

Medical Treatment

- 3 No current or prior (within 1 month of screening) medical treatment with an SGLT2i or any FDC with SGLT2i (such as SGLT2i + metformin).
- 4 If ACEi and/or ARB and/or MRA are prescribed, the dose must be stable ≥ 4 weeks before screening. Participants who have been deemed unable to tolerate ACEi or ARB therapy due to allergy or complications can be enrolled.
- 5 No current or prior treatment within 6 months prior to screening with cytotoxic therapy, immunosuppressive therapy or other immunotherapy for primary or secondary kidney disease.

Weight

- 6 Body mass index (BMI) ≤ 40 kg/m².

Sex

- 7 Male or female of non-childbearing potential.

Reproduction

- 8 Female participants must have a negative pregnancy test at screening, must not be lactating, and must be of non-childbearing potential, confirmed at screening by fulfilling one of the following criteria:
 - (a) Postmenopausal defined as amenorrhoea for at least 12 months or more following cessation of all exogenous hormonal treatments and FSH and LH levels in the postmenopausal range.

- (b) Documentation of irreversible surgical sterilisation by hysterectomy, bilateral oophorectomy, or bilateral salpingectomy but not tubal ligation.
- 9 Male participants must be surgically sterile, abstinent, or in conjunction with a female sexual partner, using a highly effective method of contraception for the duration of the study (from the time they sign consent) and for 3 months after the last dose of investigational product to prevent any pregnancies. Male study participants must not donate or bank sperm during this same time period (see Section 8.3.8.2).

Methods that can achieve a failure rate of less than 1% per year when used consistently and correctly are considered highly effective birth control methods such as:

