7 DISCONTINUATION OF STUDY INTERVENTION AND PARTICIPANT DISCONTINUATION/WITHDRAWAL

7.1 Discontinuation of Study Intervention

It may be necessary for a participant to permanently discontinue (definitive discontinuation) study intervention.

An individual participant **may be** discontinued from study intervention in the following situations:

- Participant decision. The participant is at any time free to discontinue treatment, without prejudice to further treatment.
- An AE that, in the opinion of the investigator or AstraZeneca, warrants discontinuation from further dosing.
- Severe non-compliance with the CSP.
- Safety reasons as judged by the investigator and/or sponsor where continued treatment may put participant at undue risk.

An individual participant **will be** discontinued from study intervention in the following situations:

- If BNP is increased > 100% from baseline AND is greater than 200 pg/mL; or if BNP is increased > 100% from baseline AND is greater than 400 pg/mL in a participant with atrial fibrillation.
- If the participant or male participant's partner becomes pregnant during the course of the study, investigational products should be discontinued immediately, and an AZ representative notified.
- Diabetic ketoacidosis: DKA including euglycemic DKA have been reported with use of dapagliflozin. Consider temporary interrupting study treatment if DKA is suspected. The participant should be promptly evaluated. If diabetic ketoacidosis is confirmed, investigational product(s) should be discontinued permanently. If diabetic ketoacidosis is not confirmed, restart of study intervention should be considered (see Section 7.1.1 for details).
- Symptomatic hypotension (defined as systolic BP < 90 mmHg OR diastolic BP < 60 mmHg with symptoms).
- eGFR reduction: investigational study products must be discontinued in case of confirmed eGFR reduction from baseline >50% and/or any confirmed decrease below 15 mL/min/1.73m².

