8.1.2.2 Serum Analysis of Creatinine and Cystatin C (eGFR)

Estimated GFR is another measure that is considered as a standard for assessment of kidney function. Estimated GFR is calculated based on serum creatinine values using the widely validated and accepted CKD-EPI equation. Blood samples for estimation of serum creatinine (clinical chemistry) are collected at various time points during the course of the study as shown in the SoA (Table 1).

Estimated GFR, using serum creatinine, is calculated as follows:

- $eGFR \text{ (mL/min/1.73 m}^2\text{)} = 141 \times \min(\text{SCr}/\kappa, 1)^\alpha \times \max(\text{SCr}/\kappa, 1)^{-0.209} \times 0.993 \text{ Age} \times (1.018 \text{ if female}) \times (1.159 \text{ if Black})$

Where SCr = serum creatinine (in mg/dL), κ is 0.7 for females and 0.9 for males, α is -0.329 for females and -0.411 for males, min indicates the minimum of SCr/ κ or 1, and max indicates the maximum of SCr/ κ or 1.

Alternatively, serum cystatin C provides GFR estimates that are nearly as accurate as serum creatinine adjusted for age, sex, and race thus providing an alternative GFR estimate that is not linked to muscle mass (Scholtes et al, 2020, Stevens et al, 2008). Blood samples will be collected for measurement of cystatin C, at specified time points in the SoA (Table 1).

Estimated GFR, using cystatin C, is calculated as follows:

- $eGFR = 133 \times \min(\text{S}_{\text{cys}}/0.8, 1)^{-0.499} \times \max(\text{S}_{\text{cys}}/0.8, 1)^{-1.328} \times 0.996^{\text{Age}} \times 0.932 \text{ [if female]}$

Where S_{cys} is standardised serum cystatin C (in mg/L), min indicates the minimum of $\text{S}_{\text{cys}}/0.8$ or 1, max indicates the maximum of $\text{S}_{\text{cys}}/0.8$ or 1, and age = years.

Estimated GFR calculations using the CKD-EPI formulae (in both ways, based on cystatin C and based on creatinine) will be performed by the central laboratory.

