3.2.1.3 Serum Analysis of Creatinine and Cystatin C (eGFR)

Estimated GFR is another measure that is considered as a standard for assessment of kidney function. Estimated GFR is calculated based on serum creatinine values using the widely validated and accepted CKD-EPI equation ([Levey et al, 2009](#)). Blood samples for estimation of serum creatinine (clinical chemistry) are collected at various time points during the course of the study as shown in the SoA in [Appendix A: Schedule of Activities](#).

Estimated GFR, using serum creatinine, is calculated as follows:

- $eGFR \text{ (mL/min/1.73 m}^2\text{)} = 141 \times \min(\text{SCr}/\kappa, 1)^\alpha \times \max(\text{SCr}/\kappa, 1)^{-1.209} \times 0.993^{\text{Age}} \times (1.018 \text{ if female}) \times (1.159 \text{ if Black})$

Where SCr = serum creatinine (in mg/dL), κ is 0.7 for females and 0.9 for males, α is -0.329 for females and -0.411 for males, min indicates the minimum of SCr/ κ or 1, and max indicates the maximum of SCr/ κ or 1.

Alternatively, serum cystatin C provides GFR estimates that are nearly as accurate as serum creatinine adjusted for age, sex, and race thus providing an alternative GFR estimate that is not linked to muscle mass ([Scholtes et al, 2020](#), [Stevens et al, 2008](#)). Blood samples will be collected for measurement of cystatin C, at specified time points as shown in the SoA in [Appendix A: Schedule of Activities](#).

Estimated GFR, using cystatin C, is calculated as follows:

- $eGFR = 133 \times \min(\text{S}_{\text{cys}}/0.8, 1)^{-0.499} \times \max(\text{S}_{\text{cys}}/0.8, 1)^{-1.328} \times 0.996^{\text{Age}} \times 0.932 \text{ [if female]}$

Where S_{cys} is standardized serum cystatin C (in mg/L), min indicates the minimum of $\text{S}_{\text{cys}}/0.8$ or 1, max indicates the maximum of $\text{S}_{\text{cys}}/0.8$ or 1, and age = years.

Estimated GFR calculations using the CKD-EPI formulae (in both ways, based on cystatin C and based on creatinine) will be performed by the central laboratory.

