3.2.2.5 Clinical Safety Laboratory Assessments

Blood and urine samples for determination of clinical chemistry, haematology, and urinalysis will be taken at the visits indicated in the SoA in [Appendix A: Schedule of Activities](#).

Additional safety samples may be collected if clinically indicated at the discretion of the investigator. The date, time of collection, and results (values, units, and reference ranges) will be recorded on the appropriate eCRF.

The clinical chemistry, haematology, and urinalysis will be performed at a central laboratory. Sample tubes and sample sizes may vary depending on laboratory method used and routine practice at the site.

In addition, samples will also be collected for analysis of the following parameters:

- Screening samples for parameters needed to confirm eligibility:
 - For women only: serum pregnancy test (only included in listings).
- Samples for the determination of cystatin C by a central laboratory at the visits indicated in the SoA in [Appendix A: Schedule of Activities](#).

Laboratory variables will be measured as indicated in [Table 3](#).

Table 3 Laboratory Safety Variables

Haematology/Haemostasis (whole blood) ^a	Clinical Chemistry (serum or plasma) ^a
White blood cell (WBC) count	Serum sodium (Na ⁺)
Red blood cell (RBC) count	Serum potassium (K ⁺)
Haemoglobin (Hb)	Serum urea
Haematocrit	Blood urea nitrogen (BUN)
Neutrophils absolute count	Serum creatinine
Lymphocytes absolute count	Estimated glomerular filtration rate (eGFR), calculated by CKD-EPI formula ^b
Monocytes absolute count	Uric acid
Eosinophils absolute count	Albumin
Basophils absolute count	Calcium
Platelets	Phosphate
International normalised ratio (INR) (including prothrombin time, required to calculate INR)	Alkaline phosphatase (ALP)
	Alanine aminotransferase (ALT)
Urinalysis	Aspartate aminotransferase (AST)
Glucose	Total bilirubin (TBL)
Erythrocytes	Creatinine kinase (CK)
Protein	Chloride (Cl ⁻)
Albumin	Magnesium (Mg ⁺)
Creatinine	Glucose (fasting, refer to Section 5.3.1 of the CSP)
	HbA1c (fasting, refer to Section 5.3.1 of the CSP)
Other assessments ^a	Cholesterol and lipids (fasting, refer to Section 5.3.1 of the CSP)
Cystatin C (serum)	
Serum pregnancy test (women only, at screening)	

NB. In case a participant shows an AST or ALT $\geq 3 \times$ ULN together with total bilirubin $\geq 2 \times$ ULN, refer to Appendix E in the CSP.

^a Central laboratory for all visits.

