4.11.4 Clinical Laboratory Evaluation

The following summaries will be provided:

- A summary, which will cover n, mean, SD, minimum, Q1, median, Q3, and maximum, of the observed values and change from baseline for all clinical chemistry (including cystatin C), haematology and quantitative urinalysis parameters by treatment arm and time point
- A summary of baseline to maximum observation on treatment in each clinical chemistry (including cystatin C) and haematology laboratory parameter by treatment arm (shift table)

- A summary of baseline to minimum observation on treatment in each clinical chemistry (including cystatin C) and haematology laboratory parameter by treatment arm (shift table)
- A plot of ALT versus total bilirubin, expressed as multiples of upper limit of normal (ULN)
- A plot of AST versus total bilirubin, expressed as multiples of ULN
- A summary of the number and percentage of participants reporting maximum on-treatment ALT and AST by maximum total bilirubin for assessing Hy's Law criteria
- A summary of individual participant data for participants with Potential Hy's Law i.e. participants with combined ALT or AST, and bilirubin elevations
- A summary of key participant information for participants with treatment-emergent changes in laboratory parameters (refers to clinical chemistry and haematology, other laboratory parameters are in supportive listings) outside of pre-defined criteria
- A summary of treatment-emergent laboratory changes (see [Appendix C: Treatment-Emergent Changes in Relevant Laboratory Parameters](#))
- A summary of baseline versus maximum value on treatment for urinalysis by treatment arm (shift table)
- A summary of treatment-emergent urinalysis changes

Treatment-emergent changes in relevant laboratory parameters outside pre-defined criteria for this study are provided in [Appendix C: Treatment-Emergent Changes in Relevant Laboratory Parameters](#). Treatment-emergent urinalysis changes are defined as: negative/trace at baseline to ++, +++, +++++ at any visit after baseline or an increase of at least ++, for example + to +++, ++ to +++++.

By-participant listings of all laboratory data will be provided including participant identifier, treatment, age, sex, race, visit, category, lab test name, result, change from baseline (where appropriate) and standard units. Laboratory reference ranges will also be listed and out of range values will be flagged.

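### SAP Appendix C has no eGFR criterion matching the renal stopping limits of Protocol 7.1, so a participant with baseline eGFR of 20 to about 24.5 can fall below 15 without being flagged there

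*SAP*

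**What the plan says.** Protocol 5.1 admits participants with "eGFR (CKD-EPI) ≥ 20 mL/min/1.73 m²", checked at screening. Protocol 7.1 requires study treatment to stop on "confirmed eGFR reduction from baseline >50% and/or any confirmed decrease below 15 mL/min/1.73m²". It does not say whether the creatinine or the cystatin C estimate applies, nor what counts as confirmation. The central laboratory computes both estimates, and chemistry is scheduled at every visit.

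SAP 4.11.4 plans "A summary of treatment-emergent laboratory changes" and points to Appendix C for the limits. The only renal limits there are "≥1.5xBaseline Serum Creatinine ≥2xBaseline Serum Creatinine". There is no eGFR row.

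eGFR does appear elsewhere:

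- SAP 3.2.2.5 (Table 3) lists "Estimated glomerular filtration rate (eGFR), calculated by CKD-EPI formula" as a clinical chemistry variable. It therefore falls under the SAP 4.11.4 summaries of "the observed values and change from baseline for all clinical chemistry (including cystatin C), haematology and quantitative urinalysis parameters", which include the minimum and quartiles by arm and time point. It also falls under the shift table from baseline to lowest on-treatment value, and under the listings.
- SAP 4.10.3 models change in eGFR with an MMRM.

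**The concern.** The safety table and the stopping rule measure renal harm on different scales. A fixed creatinine multiple is a fixed proportional fall in eGFR, whereas a limit of 15 is a smaller proportional fall the closer a participant starts to it. The participants with least renal reserve can therefore reach the protocol's own limit with a creatinine rise too small for Appendix C to register.

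The SAP treats the other numeric criteria of Protocol 7.1 differently. The BNP and weight/body-water criteria become the event of special interest (SAP 3.2.2.7) and are tabulated by arm (SAP 4.11.5.1). The blood pressure cut-offs appear in the vital-sign criteria (SAP 3.2.2.3) and are counted (SAP 4.11.5), though without the symptom element. eGFR is the one numeric criterion with no matching count. At stake is whether the safety report shows directly, by arm, how many participants reached a renal limit. eGFR is a secondary objective and laboratory safety is a stated safety endpoint.

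**Working it through.** The plan gives no figure on this point, so there is none to reproduce. The check asks which eGFR changes the creatinine limits capture.

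**Inputs.** Creatinine limits 1.5 and 2 (SAP Appendix C); eGFR limits of a 50% fall and 15 (Protocol 7.1); entry floor 20 (Protocol 5.1); creatinine exponent -1.209 (SAP 3.2.1.3).

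**Relation.** For one person (same age, sex and race term) with creatinine above κ, eGFR ratio = (creatinine ratio)^-1.209. Solving the full SAP equation at eGFR 20 and 15, for both sexes, both race terms and ages 40, 65 and 80, gives a creatinine ratio of 1.2686 in all 12 cases. The lowest creatinine in that check is 2.245 mg/dL, well above κ (0.7 or 0.9).

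**What the multiples mean.**

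- 1.5 times: 1.5^-1.209 = 0.6125, a fall of 38.8%.
- 2 times: 2^-1.209 = 0.4326, a fall of 56.7%.

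**Limit of 15.** The multiple needed from baseline b is (b/15)^(1/1.209). The eGFR at exactly 1.5 times is 0.6125 × b.

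| Baseline eGFR | Creatinine multiple to reach 15 | eGFR at 1.5 times | Below 15 but unflagged |
|---|---|---|---|
| 20 | 1.27 | 12.25 | above 12.25, below 15 |
| 22 | 1.37 | 13.5 | above 13.5, below 15 |
| 24 | 1.48 | 14.7 | above 14.7, below 15 |
| 25 | 1.53 | 15.3 | none |

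The crossover is 15/0.6125 = 24.49. From there upward, any fall below 15 meets the 1.5 limit. The gap is widest at the entry floor and narrows to nothing at 24.49. Eligibility uses the screening value while baseline is normally the last value on or before the first dose (SAP 4.2.2), so a baseline below 20 is possible and would widen it.

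**Limit of a 50% fall.** The multiple needed is 2^(1/1.209) = 1.77. The 1.5 row catches every such fall but pools it with falls of 38.8% to 50%. The 2 row misses falls between 50% and 56.7%.

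**Dependence on the exponent.** Protocol 8.1.2.2 prints -0.209. With that value, 1.5^-0.209 = 0.9187 and the crossover is 15/0.9187 = 16.3, below the entry floor, so the 20 to 24.5 range disappears. A fall from 20 to 15 would then need 3.96 times creatinine, and a halving of eGFR 27.6 times. Figures that extreme point to a misprint or a text-extraction fault, but the two documents still have to be reconciled.

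**The case against.** The strongest reply is that renal safety is well covered elsewhere. A reader of Appendix C alone might infer that renal safety is tabulated only as creatinine, or that renal stopping events go uncounted. The documents support neither inference.

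- eGFR has by-visit summaries, a shift to the on-treatment minimum, listings and an MMRM. The by-visit minimum shows whether anyone in an arm was below 15, though not how many.
- Protocol 8.3.5 makes a laboratory deterioration that causes discontinuation reportable as an adverse event. A participant stopped for low eGFR should therefore reach the table of adverse events leading to discontinuation by arm, and the key-information summary (SAP 4.11.3).
- A participant who met a stopping criterion but stayed on treatment falls under important deviation category 4 (SAP 4.5.2).
- It would also be too strong to say that the shift table has no category at 15. SAP 4.11.4 states no shift categories, and SAP 4.7 already derives a baseline CKD stage with a class below 15.
- Every fall of more than 50% meets the 1.5 limit, so that criterion is pooled, not missed.

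All of this stands, and it limits the point. It does not remove it. The discontinuation table is organised by system organ class and preferred term. Deviation category 4 covers all stopping criteria and only those who continued. The shift categories are unspecified, and means, quartiles and a single minimum are not counts. A reader would have to rebuild the count from listings.

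**Conclusion.** The point holds in this form: Appendix C has no eGFR criterion matching Protocol 7.1, and no planned output is specified to isolate either renal stopping criterion by arm. Under the SAP equation, a participant with baseline eGFR of 20 to 24.49 can fall below 15 with a creatinine rise of 1.27 to just under 1.5 times and meet neither creatinine limit.

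This rests on the exponent -1.209 and on the stopping rule being read on creatinine-based eGFR. If cystatin C is used, creatinine multiples do not map to the limit at all. The lack of a specified count depends on neither assumption.

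The documents do not give the share of participants with baseline eGFR of 20 to 24.5, so the number affected cannot be computed. A hidden difference between arms is a possibility, not a finding. A reader might also infer that Amendment 1 first admitted this band. The amendment history says the floor was lowered to 20 but not from what value, so that cannot be shown. The gap is one of safety reporting. It does not bear on the stopping rule itself or on the primary analysis.

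**What to change.** Add two rows to SAP Appendix C and to the treatment-emergent summary in SAP 4.11.4, by arm on the Safety Analysis Set, and keep the creatinine rows:

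- number and percentage with an eGFR fall from baseline of more than 50% at any on-treatment assessment;
- number and percentage with eGFR below 15 mL/min/1.73 m² at any on-treatment assessment.

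Three details should be settled at the same time:

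- State whether the rows use creatinine- or cystatin C-based eGFR, consistently with how Protocol 7.1 is applied.
- Show a confirmed count only under the operational definition used for Protocol 7.1, which that section does not give. The next scheduled visit should not be the default, because it can be three weeks later (for example Day 22 to Day 43) and may follow drug withdrawal, so a reversible fall would look unconfirmed.
- Reconcile the exponents in Protocol 8.1.2.2 and SAP 3.2.1.3. The 20 to 24.5 range depends on this; the added rows do not.

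Tabulating discontinuations by the Protocol 7.1 criterion met would help, because SAP 4.5.1 plans no summary of reasons for stopping study drug. It is optional given the table of adverse events leading to discontinuation.

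The cost is SAP wording and a few table rows from central laboratory data already collected. The counts may be small and should be read descriptively. No clinical rule changes.
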